8.7 Quality of Life Assessment

To quantify patient-reported quality of life outcomes in ISCHEMIA-CKD, a battery of validated instruments will be used. Angina-related quality of life will be measured by the Seattle Angina Questionnaire (SAQ); dyspnea symptoms from the Rose Dyspnea scale; the EQ-5D as a measure of overall, generic health status; and demographic items (e.g., marital status, education, perceived income). We will use these data to analyze the health status of participants in both groups over time to quantify both the magnitude and trajectory of health status recovery as a function of randomized management strategy.

8.8 Economics Assessment

As a measure of medical utilization, resource utilization data, including hospitalizations, emergency department visits, and selected cardiac procedures and tests will be collected by the Site Coordinators at each ISCHEMIA-CKD study visit or contact and entered into the main study EDC database. These data will be used to estimate and compare medical care costs from the perspective of the US healthcare system for both management strategy groups. They will also be used, along with the clinical endpoints and quality of life data, to calculate the net incremental cost and quality-adjusted life expectancy associated with the invasive strategy and the resulting within-trial incremental cost-effectiveness ratio. Details are provided in the MOO.

9. SCHEDULE OF ASSESSMENTS

Overview of Visits

All participants will undergo eligibility screening, informed consent and randomization procedures.

Follow-up in randomized participants will occur at 1.5, 3, 6, and 12 months following randomization during the first year and every 6 months thereafter, with clinic visits, phone follow-up, and other testing as described below (See [Table 2](#) for complete assessment schedule). The schedule of assessments ([Table 2](#)) specifies the preferred method of contact for each visit. Six-month visits may be via telephone or email, depending on participant stability, risk factor control, and the participant's distance from the clinic ("geography") ([see Table 2](#)). In the event that a scheduled clinic visit is not possible, to ensure participant follow-up other forms of contact should be used, such as telephone, email, communication from a personal physician, other allied health professional, or family member, or review of electronic health record or public records. After the first year, participants will be followed every 6 months until the end of the trial, at which time sites will be notified to perform a closeout visit.

Dependent on additional funding, telephone or email follow-up every 6 months or ascertainment of database information on vital status may continue after all clinic visits have been completed, unless prohibited by local regulations. At these long-term follow-up contacts, information on current health and medications, and interval hospitalizations will be collected.

Withdrawal from the Study: Complete and accurate follow-up is extremely important for the duration of the study. The participant, however, may decline to continue with their assigned management strategy at any time. This does not constitute withdrawal from the study. Participants will continue to be followed per the assessment schedule. If at any time the subject refuses to continue with study visits, every attempt will be made to continue contact by telephone, written communication, email, by proxy contact with family, friends, or allied health care providers, or record review to determine if outcome events have occurred, unless the subject specifically refuses such follow-up. National databases that record deaths will be used to ascertain vital status, unless prohibited by local regulations. The reason for (and the level of) withdrawal will be documented for all subjects withdrawn from the study or for those having limited follow-up. The subject must specify in writing what follow-up (s)he will allow, if any, at the time of withdrawal discussion.

Quality of Life (QOL) and Economics Overview

A brief set of items capturing selected interval angina and dyspnea symptoms QOL (Brief/Symptom/QOL) will be collected by the site coordinator and entered into the EDC study database at every study visit through 36 months and then each 6 months until the final closeout ISCHEMIA-CKD visit. A Hospitalization assessment as part of the main study EDC database will be collected on all randomized ISCHEMIA-CKD participants at each follow-up study interval throughout the trial to provide a measure of resource utilization.

Table 2 Schedule of Study Assessments and Procedures (see Manual of Operations for visit windows)

	Screening visit	CCTA visit	Randomization visit (Baseline Visit)	Catheterization & PCI or CABG	Follow up									
					1.5m ^A Visit 1	3m ^A Visit 2	6m ^B Visit 3	12m ^A Visit 4	18m ^B Visit 5	24m Visit 6	30m ^B Visit 7	36m ^C Visit 8	Frequency beyond 36 months	
Eligibility screen	X													
Informed consent (including biorepository consent if applicable)	X													
Creatinine and pregnancy test ^D	X													
Medical History/Medical Status	X		X		X	X	X	X	X	X	X	X	X	Q6m
Cardiovascular medications	X		X		X	X	X	X	X	X	X	X	X	Q6m
Transmit Stress Test to Core Lab ^E	X													
NYHA* and CCS class**	X		X		X	X	X	X	X	X	X	X	X	Q6m
Release for medical records signed			X				X			X		X		Q12m
Safety assessment ^F		X		X										
Vital signs, weight, height ^G			X		X	X	X	X	X	X	X	X	X	Q12m
Standard lab results ^H			X ^I			X	X	X	X	X	X	X	X	Q12m
Biorepository blood draw			X			X ^J								
Cardiac biomarkers ^K				X										
Electrocardiogram (ECG) ^L			X	X ^M			X			X				@ closeout
Lifestyle Assessment (PACE) ^{***}			X			X	X			X		X	X	Q12m
Lifestyle Counseling (PACE) ^{***}			X		X	X	X	X	X	X	X	X	X	Q6m
Modified Morisky Medication Adherence Survey			X			X	X	X	X	X	X	X	X	Q6m

Brief symptoms/QOL assessment ^N			X		X	X	X	X	X	X	X	X	Q6m
Initiate Optimal Medical Therapy (OMT)			X										
Medical Therapy Evaluation and Optimization ^O					X	X	X	X	X	X	X	X	Q6m
Schedule catheterization for INV participants ^P			X										
Hospitalization assessment					X	X	X	X	X	X	X	X	Q6m
Endpoint assessment				X	X	X	X	X	X	X	X	X	Q6m

Follow-up visits will be scheduled based on time since the date of randomization (baseline).

*NYHA- New York Heart Association **CCS- Canadian Cardiovascular Society ***PACE- Patient-centered Assessment and Counseling for Exercise and nutrition (PACE) assessment and counseling

^A 1.5, 3, and 12 month visits should be in clinic visits, depending on participant stability, risk factor control, and geography.

^B 6, 18, and 30 month visits may be via telephone, email, or in clinic depending on participant stability, risk factor control, and geography.

^C Following the 36 month visit, follow-up visits should be in clinic visits at least every 12 months. Clinic visits can be replaced by email or phone depending on participant stability, risk factor control, and geography.

^D Creatinine if not done within 90 days and pregnancy test if premenopausal.

^E Send ischemia test images (immediately following enrollment and before randomization), technical worksheets, and site interpretations/local reports from qualifying ischemia tests to core labs.

^F Safety Assessment (refer to section 13.4).

^G Height is only needed at randomization, assessments only required if visit is completed in clinic.

^H Required labs include: lipids (preferably fasting) at 3 month visit then semiannually only, and HbA1c (at visit 4, 6, 8 and annually thereafter for diabetic participants. These lab results will be requested from the participant's physician. If these results are not available they should be obtained by either the participant's treating physician or study staff. Creatinine values obtained clinically for participants with eGFR <60 at the three month follow-up visit and annually will also be recorded.

^I Additional lab required at randomization includes complete blood count Request from participant's physician, since it is expected that routine blood work will have been done within the last 6 months

^J May be requested.

^K For participants undergoing PCI: troponin and CK-MB pre-procedure and at 8-16 ± 2 hours post-PCI or at hospital discharge, whichever comes earlier. For participants undergoing CABG: troponin and CK-MB pre-procedure and at 18 ± 6 hours post-CABG. All biomarker measurements should be recorded on eCRF. A biomarker measurement should be obtained before and after all PCI and CABG procedures, whenever possible.

^L Send to ECG core lab; ECG required for all cardiac admissions and revascularizations; year 1 ECG optional (filed on site) and closeout.

^M ECG done following procedure (60±30 mins post-PCI, 3 days post-CABG).

^N Selected Seattle Angina Questionnaire/Rose dyspnea scale/EQ-5D.

^O At every follow-up visit the research team, in collaboration with the treating physician(s), will evaluate effectiveness of medical therapy and optimize guideline recommendations and study algorithms.

^P Planned cath and revascularization only in the INV group. See MOO for time windows for performing cath and revascularization after randomization. Optimal revascularization treatment should be targeted within 30 days after randomization in the Invasive strategy group. In the Conservative group, revascularization is reserved for participants with refractory angina symptoms or acute ischemic events.

Screening visit

- Patients with advanced CKD and at least moderate ischemia (see protocol [appendix A](#)) will be assessed as potential study candidates
- General medical and cardiac history will be reviewed for eligibility according to the inclusion/exclusion criteria in [section 4.3](#)
- Willingness of both the prospective participant and their physician for participation throughout the study will be confirmed
- All screened prospective participants will be recorded in the paper screening log
- Prospective participants meeting clinical and site-based ischemia inclusion and exclusion criteria and interested in participating in the study will be consented for the study
- Consented participants will receive a study ID number via IVRS/IXRS. These participants are considered “enrolled” (not randomized).
- Creatinine testing if it has not been done within the last 90 days
- Pregnancy test if premenopausal
- For enrolled participants ischemia tests will be transferred electronically to the appropriate core laboratory. (see [section 5.4](#))

Randomization visit (Baseline Visit) (targeted within 15 days of participant’s consent)

- Medical history including CV medications will be documented
- NYHA and CCS class (see MOO)
- Brief symptoms/QOL assessment will be collected (prior to actual randomization)
- Modified Morisky medication adherence survey (see MOO)
- Vital signs, height and weight will be measured
- 12 lead ECG will be performed and sent to ECG core lab; stress ECG, and symptom, and hemodynamic results will be sent to ECG core lab
- Results of routine laboratory tests performed within 6 months of visit will be recorded, including HbA1c for diabetic participants. If these test results are not available a blood draw for routine laboratory tests will be done at this visit (see MOO)
- Baseline blood draw for biomarker/genetics biorepositories

- Eligible participants will be randomized to INV or CON strategies via the IVRS/IXRS system. (These participants are considered randomized)
- Participants randomized to INV strategy should target to undergo catheterization, with optimal revascularization to be completed within a target of 30 days from randomization
- PACE will be implemented for all participants
- Initiate OMT in all randomized participants according to guideline recommendations and study algorithms

Cath and Revascularization for participants randomized to INV strategy (protocol assigned); also applies to all revascularization procedures for participants in both management strategies

- For protocol assigned cardiac cath and revascularization (INV strategy participants), target completion within 30 days of randomization
- Revascularization to be performed as per Optimal Revascularization Therapy (ORT) (refer to MOO)
- For participants undergoing PCI
 - 12 lead ECG to be performed post-PCI at 60 ± 30 minutes, and as needed for chest pain
 - Blood draw for both CK-MB and troponin before PCI, and at 8-16 ± 2 hours post-PCI or at hospital discharge, whichever comes earlier, whenever possible
 - All pre- and post-procedure biomarker measurements that are obtained should be recorded on eCRF
- For participants undergoing CABG
 - 12 lead ECG to be performed on day 3 post-CABG or at hospital discharge whichever comes earlier, and as needed for chest pain
 - All pre- and post-procedure operative biomarker measurements that are obtained should be recorded on eCRF

1.5 month (6 week) visit (Visit 1)

- Medical status assessment
- NYHA and CCS class (see MOO)
- Vital signs and weight will be measured
- Lifestyle counseling as per PACE will be performed
- Brief symptoms/QOL assessment will be collected

- Hospitalization assessment will be collected
- Endpoints will be assessed
- The study team, in collaboration with the treating physician(s), will evaluate effectiveness of medical therapy and optimize as needed according to guideline recommendations and study algorithms

3 month visit (Visit 2)

- Medical status assessment
- NYHA and CCS class (see MOO)
- Vital signs and weight will be measured
- Lifestyle assessment and counseling as per PACE will be performed
- Brief symptoms/QOL assessment will be collected
- Hospitalization assessment will be collected
- Biorepository blood draw may be performed if additional funding is obtained
- Endpoints will be assessed
- Obtain lab results from participant's treating physician for lipids (preferably fasting). If not available these tests should be obtained by the participant's treating physician or the study staff. Creatinine values obtained clinically will be recorded.
- The study team, in collaboration with the treating physician(s), will evaluate effectiveness of medical therapy and optimize as needed according to guideline recommendations and study algorithms

6/18/30 month visits (Visits 3, 5, 7 respectively)

- Medical status assessment
- NYHA and CCS class (see MOO)
- Vital signs and weight will be measured (only if clinic visit)
- Modified Morisky medication adherence survey (see MOO)
- Lifestyle counseling as per PACE will be performed
- Brief symptoms/QOL assessment will be collected

- Hospitalization assessment will be collected
- Endpoints will be assessed
- Obtain lab results from participant's treating physician for lipids (preferably fasting). If not available lipid tests should be obtained by the participant's treating physician or the study staff.
- The study team, in collaboration with the treating physician(s), will evaluate effectiveness of medical therapy and optimize as needed according to guideline recommendations and study algorithms

12/24/36 month visits (Visits 4, 6, 8 respectively)

- Medical status assessment
- NYHA and CCS class (see MOO)
- Vital signs and weight will be measured
- 12 lead ECG will be performed and submitted to core lab only at 24 month visit. Optional ECG to be retained at site at 12 months
- Modified Morisky medication adherence survey (see MOO)
- Lifestyle assessment and counseling as per PACE will be performed
- Brief symptoms/QOL assessment will be collected
- Hospitalization assessment will be collected
- Endpoints will be assessed
- Obtain lab results from participant's treating physician for lipids (preferably fasting) and HbA1c for diabetic participants. If not available lipid tests should be obtained by the participant's treating physician or the study staff. Creatinine values obtained clinically for will also be recorded.
- The study team, in collaboration with the treating physician(s), will evaluate effectiveness of medical therapy and optimize as needed according to guideline recommendations and study algorithms

Continuing Follow-Up Visits (every 6 months following the 36 month visit until close out)

- Medical status assessment
- NYHA and CCS class (see MOO)

- Vital signs, and weight (only at every 12 month clinic visit)
- Modified Morisky medication adherence survey
- Lifestyle assessment as per PACE (only at every 12 month visit)
- Lifestyle counseling as per PACE
- Brief symptoms/QOL assessment will be collected
- Hospitalization assessment will be collected
- Endpoint will be assessed
- Obtain lab results from participant's treating physician for lipids (preferably fasting). If not available lipid tests should be obtained by the participant's treating physician or the study staff.
- The study team, in collaboration with the treating physician(s), will evaluate effectiveness of medical therapy and optimize as needed according to guideline recommendations and study algorithms

Close out visit (in addition to all assessments for the regularly scheduled visit)

- 12 lead ECG will be performed and submitted to core lab
- Obtain lab results from participant's treating physician for lipids (preferably fasting) and HbA1c for diabetic participants. If not available from the participant's treating physician these tests should be obtained by the participant's treating physician or the study staff.

10. ADJUDICATION OF CLINICAL EVENTS

An independent clinical event adjudication committee (CEC) will review and adjudicate all primary endpoint events and selected secondary endpoints in a blinded fashion based on study definitions. Endpoints to be adjudicated include death (including cause), myocardial infarction, resuscitated cardiac arrest, hospitalization for unstable angina, hospitalization for heart failure, and stroke. Because the trial is not blinded, to mitigate bias in the ascertainment of events, several strategies will be used to identify (“trigger”) all suspected endpoints in all participants including carefully constructed data collection tools that focus sites on key endpoint events, screening of ECG core lab data, site investigator and coordinator education about CEC procedures, and processing of events found by physicians during review of source documents pertaining to already identified endpoints. Care will be taken to blind reviewers to any information that could identify the participant or could reveal the randomized management strategy assignment. CEC members do not have access to management strategy assignment in order to avoid bias, which is an important process issue in this unblinded trial.

11. STATISTICAL CONSIDERATIONS AND ANALYSIS PLAN

11.1 Sample Size Determination and Statistical Power

11.1.1 Summary of Power and Precision

As shown in Tables 3 and 4 below, the planned sample size of approximately 1,000 randomized participants will result in an estimate of the hazard ratio that differs from the true hazard ratio by no more than a factor of 1.19 with 95% probability and will yield power $\geq 80-95\%$ for comparing the primary composite endpoint across the two randomized groups assuming the 4-year cumulative rate of the primary composite endpoint is 60% in participants randomized to CON strategy and is less by a factor of 15% to 19% (relative reduction) in participants randomized to INV strategy. Power and precision under other assumptions are summarized in [Table 5](#) and [Table 6](#) below.

CON anticipated 4-year event rate	Power		
	$\Delta = 0.15$	$\Delta = 0.17$	$\Delta = 0.19$
Event %			
45%	56	67	76
50%	64	75	84
55%	73	83	90
60%	81	90	95
65%	88	95	98
70%	94	98	99

NOTE: Δ denotes relative reduction in 4-year event rate in INV vs. CON groups. **Assumptions:** Two-sided log-rank test with $\alpha = 0.05$; 500 participants per group; average follow-up 3.7 years; loss-to-follow-up 1% per year; survival times follow exponential distribution.

CON anticipated 4-year event rate	Margin of Error (MOE)		
	$\Delta = 0.15$	$\Delta = 0.17$	$\Delta = 0.19$
Event %			
45%	1.22	1.22	1.23
50%	1.21	1.21	1.21
55%	1.20	1.20	1.20
60%	1.19	1.19	1.19
65%	1.18	1.18	1.18
70%	1.17	1.18	1.18

NOTE: Margin of Error is the anti-log of the expected half-width of the 95% confidence interval for the log-hazard ratio. Assumptions: Based on a univariable Cox model with a binary treatment indicator and Wald-type 95% confidence intervals.

11.2 Statistical Analysis Plan

All major treatment comparisons between the randomized groups will be performed according to the principle of "intent-to-treat;" that is, participants will be analyzed (and endpoints attributed) according to the randomized strategy, regardless of subsequent invasive testing or treatment. Statistical comparisons will be performed using two-sided significance tests. A statistical analysis plan will be finalized before trial completion and data analysis.

11.2.1 Analysis of the Primary Endpoint

The statistical comparison of the two randomized groups with respect to the primary composite endpoint will be a "time-to-event" analysis, and will therefore be based on the time from randomization to the first occurrence of any of the components of the primary composite endpoint (death or nonfatal MI). The Cox proportional hazards will be the primary analytic tool for assessing outcome differences between the two randomized groups. To preserve power in the face of participant heterogeneity, the overall comparison may be adjusted for a selected set of prognostically important baseline covariates that will be carefully defined and pre-specified in the statistical analysis plan. The level of significance for the assessment of the primary endpoint will be $\alpha=0.05$. In addition to Cox regression, event-free survival probabilities will be estimated as a function of follow-up time in each treatment group using the Kaplan-Meier method and presented with point wise 95% confidence intervals. If the data provide evidence of an overall difference in outcome between management strategy groups, we will further examine whether the therapeutic effect is similar for all participants, or whether it varies according to specific participant characteristics, which will be pre-specified in the statistical analysis plan.

11.2.2 Analysis of the Secondary Endpoints

Secondary endpoints that will be evaluated include: (1) quality of life as measured by the SAQ Angina Frequency Scale and SAQ Quality of Life Scale; (2) composite of cardiovascular death, nonfatal myocardial infarction, or stroke; (3) composite of cardiovascular death, nonfatal MI, resuscitated cardiac arrest, or hospitalization for unstable angina or heart failure; (4) all-cause death; (5) CV death (6) MI; (7) resuscitated cardiac arrest; (8) hospitalization for unstable angina; (9) hospitalization for heart failure; (10) stroke; (11) composite of cardiovascular death, nonfatal MI, stroke, resuscitated cardiac arrest, or hospitalization for unstable angina or heart failure; and (12) health resource utilization, cost, and cost effectiveness. Plans for the analysis of the quality of life and economic endpoints are addressed below in [Sections 11.2.4](#) and [11.2.5](#). For other secondary endpoints, analysis will be similar to the primary endpoint, using time from randomization until the first occurrence of the specific secondary endpoint as the response variable.

Unambiguous operational definitions of each study endpoint will be documented in the Clinical Event Committee Charter and statistical analysis plan before performing unblinded analysis. For MI we will specify a primary definition (adapted from the universal definition of MI³²; to be used in the primary analysis of the primary and secondary endpoints). Other definitions (to be used in secondary analyses) will include the universal definition of MI and criteria to categorize large infarctions. Data collection instruments and the adjudication process will allow construction of alternative endpoint MI definitions.

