	
significant unprotected left main stenosis
 
 • Enrolled in a competing trial that involves a non-approved cardiac drug or device • Inability to comply with the protocol • Exceeds the weight or size limit for cardiac catheterization at the site • Canadian Cardiovascular Society Class III angina of recent onset, OR angina of any class with a rapidly progressive or accelerating pattern • Canadian Cardiovascular Society Class IV angina, including unprovoked rest angina • High risk of bleeding which would contraindicate the use of dual antiplatelet therapy • Cardiac transplant recipient • Prior CABG, unless CABG was performed more than 12 months ago, and coronary anatomy has been demonstrated to be suitable for PCI or repeat CABG to accomplish complete revascularization of ischemic areas (CCC approval required)
Primary Endpoint	Time to first occurrence of death or nonfatal myocardial infarction.
Secondary Endpoints	
 • Angina control per SAQ Angina Frequency Scale • Disease-specific quality of life per SAQ Quality of Life Scale • Composite of cardiovascular death, nonfatal myocardial infarction, or stroke • Composite of cardiovascular death, nonfatal myocardial infarction, resuscitated cardiac arrest, or hospitalization for unstable angina or heart failure • All-cause death • Cardiovascular death • Nonfatal MI • Resuscitated cardiac arrest • Hospitalization for unstable angina • Hospitalization for heart failure • Stroke • Composite of cardiovascular death, nonfatal myocardial infarction, stroke, resuscitated cardiac arrest, hospitalization for unstable angina

	
or heart failure.
 
 • Health resource utilization, costs, and cost-effectiveness
Assessment Schedule	Pre-eligibility screening, randomization, 1.5 months, 3 months, 6 months, 12 months, and every 6 months thereafter.
Study Duration	Enrollment will occur over approximately 3.5 years with an expected minimum of 18-24 months follow-up and an average of approximately 4 years follow-up.
Clinical Event Adjudication Committee	The following events will be adjudicated by a blinded Clinical Event Adjudication Committee: death, myocardial infarction, resuscitated cardiac arrest, hospitalization for unstable angina, hospitalization for heart failure, and stroke.

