2. BACKGROUND AND RATIONALE

Among patients with advanced CKD, cardiovascular disease is the leading cause of death,^{1,2} 15-30 times higher than the age-adjusted cardiovascular mortality rate in the general population.^{3,4} The projected 4-year mortality is >50% in patients with advanced CKD⁵⁻⁹ and is worse than that for patients in the general population who have cancers, heart failure, stroke or MI.¹⁰ Participants with advanced CKD are 5-10 times more likely to die than to reach end stage renal disease (ESRD).¹¹ Despite this, ~80% of contemporary coronary artery disease (CAD) trials exclude participants with advanced CKD.¹² Most of the treatments aimed at reducing cardiovascular events in advanced CKD are therefore extrapolated from cohorts without advanced CKD. Participants with advanced CKD and cardiovascular disease are undertreated with less frequent use of statins and revascularization therapies, and the optimal management approach to these patients is unknown. Participants with advanced CKD are notably underrepresented in contemporary trials comparing revascularization with medical therapy in SIHD patients, such as the Bypass Angioplasty Revascularization Investigation 2 Diabetes (BARI 2D) trial¹³ or the Clinical Outcomes Utilizing Revascularization and Aggressive Drug Evaluation (COURAGE) trial,¹⁴ making any assessment about the efficacy of revascularization plus medical therapy vs. initial medical therapy alone in this cohort problematic.

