An additional key parameter for interim monitoring will be the frequency of early catheterization among participants randomized to the CON strategy. Such catheterizations will be classified according to (1) whether the catheterization was allowed by the protocol (e.g. for documented refractory symptoms) and (2) whether the catheterization was preceded by a nonfatal primary endpoint event (i.e., MI). A pattern of frequent early catheterization in CON participants without prior endpoint events would suggest that the study may have difficulty achieving high statistical power. Moreover, if this was due to frequent protocol violations, then a finding of no treatment effect may be challenging to interpret. To address these concerns, rates of early catheterization in the CON group will be analyzed and reported, with a focus on estimating the probability that a CON participant will undergo catheterization within a specified time interval and before an endpoint event. To obtain this probability, the distribution of "time from randomization to catheterization" for CON participants will be estimated using the cumulative incidence function method for competing risks.³⁷ For this latter analysis participant follow-up will be censored at the last contact date or terminated after the participant's first primary endpoint event, whichever occurs first.

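### Section 11.2.2 applies the primary-endpoint analysis to nine secondary endpoints that omit some or all deaths; on the natural reading, Kaplan-Meier would overstate their absolute event rates

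*Combined protocol and SAP*

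**What the plan says.** Section 11.2.2 lists ten clinical time-to-event secondary endpoints (items 2 to 11) and gives one rule for analysing them: "For other secondary endpoints, analysis will be similar to the primary endpoint, using time from randomization until the first occurrence" of the endpoint concerned. The single-event items run "5) CV death (6) MI; (7) resuscitated cardiac arrest; (8) hospitalization for unstable angina; (9) hospitalization for heart failure; (10) stroke".

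Section 11.2.1 sets out the primary analysis. Cox regression is the main tool for comparing arms, and in addition "event-free survival probabilities will be estimated as a function of follow-up time in each treatment group using the Kaplan-Meier method", with pointwise 95% confidence intervals. The primary endpoint is death from any cause or nonfatal MI.

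One competing-risk method appears in the document. In section 11.2.6, time to catheterization in the CON arm "will be estimated using the cumulative incidence function method for competing risks". That analysis is for interim monitoring only.

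Section 11.2 leaves a full statistical analysis plan to be completed before data analysis. Section 10 has cause of death adjudicated by the blinded events committee.

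**The concern.** Kaplan-Meier gives a valid event probability for the primary endpoint because a death is itself an event there. Of the ten secondary endpoints, only all-cause death (item 4) shares that property. Four count cardiovascular death only (items 2, 3, 5 and 11), so non-cardiovascular death competes. Five are single events with no general death component (items 6 to 10), so deaths compete.

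If competing deaths are censored, Kaplan-Meier treats people who have died as still able to have the event later. One minus Kaplan-Meier then exceeds the proportion of randomized participants who actually have it. This population has high mortality, so the gap need not be small.

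What is at stake is the absolute rates and curves by arm, and any absolute risk difference read from them. The distortion also varies by endpoint: it is larger where no deaths are counted and smaller for CV death and its composites. Rates across the secondary endpoints would then not be comparable with one another.

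**Working it through.** **1. The plan's own figures.** Section 11.1.1 gives power "assuming the 4-year cumulative rate of the primary composite endpoint is 60% in participants randomized to CON strategy", with 500 per arm, 3.7 years of follow-up, 1% annual loss and exponential survival.
- CON hazard: -ln(0.40)/4 = 0.2291 per year.
- A 15% relative reduction gives an INV rate of 0.60 × 0.85 = 51%, so HR = ln(0.49)/ln(0.40) = 0.779.
- Expected events are 519, and the Schoenfeld power is 81.4% (stated: 81%).
- At reductions of 17% and 19%, power is 89.7% and 95.0% (stated: 90% and 95%).
- The margin of error is 1.189 to 1.191 (stated: 1.19).

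The plan's arithmetic reproduces, so the hazard 0.2291 is used below. The plan states no figure for any secondary endpoint.

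**2. Inputs that are assumptions.** The background section says "The projected 4-year mortality is >50% in patients with advanced CKD". That is a general figure, and the exclusions in section 4.3.1 (limited life expectancy, LVEF below 35%, NYHA class III-IV) may lower it. I therefore use 4-year mortality M of 30% to 50%. The document gives neither the split of deaths by cause nor rates for the other single events.

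**3. Formulas**, with event hazard h, competing death hazard c and T = 4 years:
- 1-KM = 1 - exp(-4h)
- Cumulative incidence = h/(h+c) × [1 - exp(-4(h+c))]

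**4. MI, with the 60% composite held.** Let d be the death hazard before MI and k·d the death hazard after it. Then h + d = 0.2291, and d is solved so that 4-year survival equals 1 - M:

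exp(-4(h+d)) + h × [exp(-4kd) - exp(-4(h+d))]/(h + d - kd) = 1 - M.

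With c = d, cumulative incidence reduces to 0.60 × h/0.2291.

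| M | k | d | h | 1-KM | Cumulative incidence | Ratio |
|---|---|---|---|---|---|---|
| 50% | 1 | 0.1733 | 0.0558 | 20.0% | 14.6% | 1.37 |
| 50% | 2 | 0.1557 | 0.0734 | 25.4% | 19.2% | 1.32 |
| 50% | 4 | 0.1260 | 0.1031 | 33.8% | 27.0% | 1.25 |
| 40% | 1 | 0.1277 | 0.1014 | 33.3% | 26.6% | 1.26 |
| 40% | 4 | 0.0800 | 0.1491 | 44.9% | 39.1% | 1.15 |
| 30% | 1 | 0.0892 | 0.1399 | 42.9% | 36.6% | 1.17 |
| 30% | 4 | 0.0509 | 0.1781 | 51.0% | 46.7% | 1.09 |

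(Results use unrounded hazards.) The overstatement is 9% to 37% in relative terms, or about 4 to 7 points.

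**5. A rarer single event.** If 1-KM is 5% (h = 0.0128) and the event does not change later mortality, cumulative incidence is 4.2% at M = 30% and 3.6% at M = 50%.

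**6. CV death.** Let D = -ln(1-M)/4 and s = the non-cardiovascular share of deaths, so h = (1-s)D and c = sD.
- M = 30%, s = 0.2: 24.8% against 24.0%, 0.8 points.
- M = 50%, s = 0.2: 42.6% against 40.0%, 2.6 points.
- M = 50%, s = 0.3: 38.4% against 35.0%, 3.4 points.

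**7. Difference between arms.** Take M = 50%, k = 1 and an assumed hazard ratio of 0.776, close to the 0.779 in step 1.
- If it applies to both MI and death, INV is 15.9% by 1-KM and 12.4% by cumulative incidence. The differences from CON are 4.1 points (20.0 - 15.9) and 2.2 points (14.6 - 12.4).
- If it applies to MI only, the differences are 4.1 and 3.0 points.
- If it applies to death only, 1-KM shows no difference, while MI cumulative incidence is 1.0 point higher in INV (15.6% against 14.6%).

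**The case against.** The strongest reply is that no error has been shown. The rule in section 11.2.2 says similar, not identical, and the one feature it spells out is the response variable. In section 11.2.1 Cox regression is the main tool and Kaplan-Meier is an addition under the primary endpoint. No sentence commits to reporting one minus Kaplan-Meier for the nine endpoints. Section 11.2 leaves a full analysis plan to come, and section 11.2.6 shows that the authors know the cumulative incidence function.

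Much of this stands. A reader might infer that the trial has decided to censor these deaths; the document does not say so, and the reading remains an inference. It is still the natural one. Section 11.2.2 explicitly defers endpoint definitions but gives its own rule for the analysis, and an analyst following that rule would carry Kaplan-Meier over. The competing-risk method is tied to CON catheterization alone.

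Three other stronger readings fail:
- **That the treatment comparison is invalid.** A Cox model that censors at the competing death still estimates a cause-specific hazard ratio. No stopping guide uses these curves either, since interim comparisons focus on all-cause mortality and the primary composite.
- **That the endpoints are left undefined.** Section 11.2.2 lists MI, whereas the synopsis has "All-cause death • Cardiovascular death • Nonfatal MI • Resuscitated cardiac arrest". But the same section promises: "Unambiguous operational definitions of each study endpoint will be documented in the Clinical Event Committee Charter and statistical analysis plan". The count of nine holds under either wording.
- **That 37% is the general size.** It needs 50% mortality and no rise in death hazard after MI. The document gives no rates for stroke, arrest or the hospitalizations from which to fix their size.

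**Conclusion.** The point holds as a gap in specification whose natural reading leads to the wrong estimator for absolute risk. The direction needs no numerical assumption: whenever uncounted deaths precede the event and are censored, one minus Kaplan-Meier exceeds cumulative incidence. The size rests on constant hazards, 4-year mortality of 30-50%, a death hazard after MI of 1 to 4 times that before, and the planned 60% composite. On those terms MI is overstated by about 9% to 37%. CV death is overstated by about 1 to 3 points if 20-30% of deaths are non-cardiovascular. Absolute differences between arms can also shift, by an amount that depends on how treatment affects death as well as the event.

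The consequence is confined to absolute rates, curves and risk differences for nine secondary endpoints. It should be fixed before analysis but does not threaten the trial's main conclusion.

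**What to change.** Add to section 11.2.2 or the statistical analysis plan:
- For every secondary time-to-event endpoint that does not include all-cause death, event rates by arm will be estimated with the cumulative incidence function already named in section 11.2.6, with 95% confidence intervals.
- Any death not counted in that endpoint's definition is the competing event. For CV death and its three composites this is non-cardiovascular death.
- The Cox model remains the treatment comparison, and its hazard ratio is labelled cause-specific.

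The cost is a few sentences and slightly lower reported rates. No new data are needed, because cause of death is already adjudicated, and the design and power are unchanged.
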